8.0 Efficacy Analyses

8.1 General Considerations

All efficacy analyses will be conducted in the FAS Population.

Unless otherwise specified, during the 12-month placebo-controlled Treatment Period, the analyses of efficacy endpoints will only include data from the placebo group and elagolix plus E2/NETA group; elagolix plus E2/NETA group will be compared against placebo. Statistical tests will be conducted at an alpha level of 0.05 (two-sided). A test will be deemed significant if the P value rounded to three decimal places is less than or equal to 0.05 unless otherwise specified.

In addition, efficacy endpoints collected during each of the placebo-controlled and open-label Treatment Periods will also be summarized as observed cases (by treatment group); no comparisons or statistical tests will be performed.

The primary and secondary analyses will be performed after all ongoing subjects have completed the 12-month placebo-controlled Treatment Period and the database has been locked. This will be the only and final analysis for the co-primary and key secondary efficacy endpoints as well as all other efficacy endpoints collected in the 12-Month Placebo-Controlled Treatment Period.

Unless otherwise specified, categorical data will be summarized by frequencies and percentages; continuous data will be summarized by the mean, standard deviation, median, minimum, and maximum. For the analyses of change from baseline, the within-group changes will be summarized with the mean, standard deviation or standard error,

and 95% confidence intervals (CIs); between-group differences will be summarized with the mean, standard error, P value (as appropriate), and the 95% CIs.

For efficacy variables collected using the daily e-Diary, the baseline will be based on the average of the last 35 calendar days during the Screening Period prior to and including Study Day 1. For other efficacy variables, the baseline during the 12-month placebo-controlled Treatment period (Months 1 – 12) will be the last non-missing value obtained prior to or on Study Day 1. The baseline during the open-label Treatment Period (Months 13 – 48) will be the last non-missing value obtained prior to or on the initiation day of elagolix (either elagolix alone or elagolix plus E2/NETA).

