8.1.1 General Considerations

The SAS system will be used to perform the statistical analyses. All statistical tests will be two-sided and a significance level of 0.05 will be used unless otherwise specified. A test will be deemed statistically significant if the *P* value rounded to three decimal places is less than or equal to 0.050 unless otherwise specified. The primary safety and efficacy comparisons will be between the elagolix plus E2/NETA treatment group and the placebo group. Data from subjects randomized to elagolix 200 mg BID alone will be summarized separately from subjects randomized to the elagolix 200 mg BID plus E2/NETA (1 mg/0.5 mg) QD arm. Unless otherwise specified, no statistical tests will be performed to evaluate potential differences between the two elagolix dose groups.

Data collected during the treatment period will be summarized by randomized treatment assignment on study Day 1.

- Subjects randomized to elagolix plus E2/NETA in the first 12 months of treatment.
- Subjects randomized to elagolix alone in the first 6 months of treatment
- Subjects randomized to placebo in the first 12 months of treatment

Analysis details will be specified in the statistical analysis plan. No statistical tests will be performed to evaluate potential differences between dose groups following the 12 month placebo-controlled portion of the 48-month Treatment Period.

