8.3.3 Primary Efficacy Analysis

The primary null hypothesis for this study is that there is no difference in the proportion of responders for each co-primary efficacy endpoint at Month 6 between elagolix plus E2/NETA and placebo. The null hypothesis will be tested against the alternate hypothesis that there is a difference between elagolix plus E2/NETA and placebo in the proportion of responders for each co-primary efficacy endpoint at Month 6.

Elagolix plus E2/NETA will be considered statistically more efficacious than placebo for the co-primary endpoint if and only if the two-sided P value for the comparison of the proportion of responders for both DYS and NMPP is less than or equal to 0.05 and in favor of elagolix plus E2/NETA.

The primary analysis of each of the co-primary endpoints will be based on a logistic regression model with the responder/non-responder categorization as the dependent variable, treatment as the main effect, and baseline pain score (DYS or NMPP) as the covariate. Elagolix plus E2/NETA will be compared to placebo for each of the co-primary endpoints. The proportion of responders, difference in proportions between each elagolix group and placebo, and odds ratio with corresponding 95% confidence intervals (CIs) and P values will be presented.

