10.0 Overall Type-I Error Control

The primary comparison for the co-primary will be made between elagolix plus E2/NETA and placebo. The elagolix alone arm will be served as a reference arm. Therefore, no adjustment of the type I error rate (alpha) for the primary endpoint is needed. Ranked secondary endpoints will be tested following a fixed-sequence testing procedure. Specifically, testing will begin with testing each of the co-primary endpoints using alpha of 0.05 (2-sided) for elagolix plus E2/NETA compared to placebo. If both co-primary endpoints achieve statistical significance with elagolix W2/NETA as compared to placebo, continued testing will be performed for the ranked secondary endpoints following a fixed-sequence testing procedure.

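### Significance is judged by default on a P value rounded to three decimals, so the ranked secondary tests run at 0.0505 rather than the stated 0.05, and the rule for the co-primaries is unclear (minor)

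*SAP*

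**What the plan says.** - **Protocol 8.1.1:** "All statistical tests will be two-sided and a significance level of 0.05 will be used unless otherwise specified". The next sentence makes a test significant if its P "value rounded to three decimal places is less than or equal to 0.050 unless otherwise specified".
- **SAP 8.1:** sets the same two-sided 0.05 level for the efficacy analyses. Its next sentence has a test "deemed significant if the P value rounded to three decimal places is less than or equal to 0.05", with the same closing proviso for exceptions.
- **SAP 8.3.3:** the co-primary claim succeeds only if the two-sided P value "for both DYS and NMPP is less than or equal to 0.05 and in favor of elagolix plus E2/NETA". Rounding is not mentioned.
- **SAP 10.0 and Protocol 8.1.6.4:** the co-primary level is given as 0.05 and 0.050 respectively.
- **Ranked secondaries:** SAP 3.2 lists 14 in order and SAP 10.0 sends them through a fixed sequence. SAP 8.4.1.1 and 8.4.1.2 report a P value and a 95% CI for each. None of these sections states a significance criterion of its own. Protocol 8.1.6.2 says that the procedure maintains the family-wise type I error rate.

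No section says that unrounded P values are used for decisions, and none lowers the cut-off to offset the rounding.

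**The concern.** The rounding sentence is a decision rule, because it defines when a test counts as significant. It is not a display convention. A P value of 0.0504 rounds to 0.050 and passes, so each document states a level that its own default rule does not hold. Two things are at stake.

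1. **Ranked secondaries.** Each result decides whether the next rank may be tested. A P value just above 0.05 would let testing go on when a test at the stated level would stop it, and the 95% CI printed beside it would include no effect.
2. **Co-primaries.** The general rule rounds unless something else is specified, and the specific rule in SAP 8.3.3 is silent on rounding. A reader cannot tell whether a co-primary P of 0.0503 is a success or a failure.

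**Working it through.** **Inputs.** Level 0.05 two-sided and the rounding rule (Protocol 8.1.1, SAP 8.1). Planned sizes 400 and 200. Responder rates 54% against 35% for NMPP and 59% against 23% for DYS. Stated power above 90% (Protocol 8.2, SAP 2.4).

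**1. The plan's own figure.** Pooled-variance normal approximation, with zβ = (Δ − z·SE₀)/SE₁.

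NMPP:
- Pooled rate = (0.35×200 + 0.54×400)/600 = 0.4767
- SE₀ = √[0.4767×0.5233×(1/200 + 1/400)] = 0.04325
- SE₁ = √[0.35×0.65/200 + 0.54×0.46/400] = 0.04193
- zβ = (0.19 − 1.9600×0.04325)/0.04193 = 2.509, so power is 0.99395

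The same steps for DYS give power above 99.99%. The claim of more than 90% is reproduced.

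**2. The cut-off that the rule implies.**

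| P | Rounded | At or below 0.050? |
|---|---|---|
| 0.0501 | 0.050 | yes |
| 0.05049 | 0.050 | yes |
| 0.050499999 | 0.050 | yes |
| 0.0505 | 0.051 | no |

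The rule rejects for P < 0.0505. If P is uniform under the null, the level is 0.0505, or 0.02525 per side, with critical |z| 1.9557 instead of 1.9600. The excess is 0.0505 − 0.0500 = 0.0005, and 0.0005/0.05 = 1% relative. In 20 million simulated uniform P values the rounding rule rejected 0.05057 of the time and P ≤ 0.05 rejected 0.05007, a difference of 0.0005.

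**3. Family-wise error.** Both co-primaries must pass, so if one null is true, a false co-primary claim needs that null to be rejected: probability at most 0.0505. After that, any false rejection in a fixed sequence requires rejection of the first true null in the order, again with probability at most 0.0505. The worst case over the whole family is 0.0505, reached once.

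**4. Test against interval.** For an estimate with z = estimate/SE, the lower 95% limit is (z − 1.9600)·SE. For any z between 1.9557 and 1.9600 this is negative. At z = 1.957, for example, it is −0.003·SE. The rounded test is significant and the interval includes no effect.

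**5. Power cost of removing the rounding.**
- NMPP at level 0.0505: zβ = (0.19 − 1.9557×0.04325)/0.04193 = 2.514, power 0.99403.
- The loss is 0.994025 − 0.993950 = 0.000075, or 0.0075 percentage point.
- DYS power stays above 99.99%, and the sample size does not change.
- The documents give no planning assumptions for the secondaries. For a unit-variance normal statistic the loss cannot exceed (1.9600 − 1.9557)×0.399 = 0.0017, or 0.17 percentage point.

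**The case against.** The strongest case on the other side has four parts.

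1. **SAP 8.3.3 may already override the rounding.** The general sentence in each document gives way where something else is specified, and SAP 8.3.3 sets a specific condition for the co-primaries without rounding. That is a fair reading. A reader might infer that every test, co-primaries included, runs at 0.0505; the documents do not establish that. But SAP 8.3.3 does not say that the P value is unrounded either, so the co-primary rule is unclear. No comparable wording covers the ranked secondaries, where the default rule stands.
2. **The rule is open, prespecified and the same in both documents.** True. It creates no analyst discretion and suggests no concealment. It still does not match the level stated beside it.
3. **The P values are approximate.** They come from logistic regression, ANCOVA and an MMRM whose covariance structure is chosen by AIC. True, and unrounded P values would not guarantee a level of exactly 0.0500. The rounding adds 0.0005 to the nominal cut-off whatever the quality of the approximation.
4. **The practical effect is very small.** True. With planned co-primary power above 99%, a borderline P there is unlikely.

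Two further readings are tempting and do not hold. A reader might infer that 1% is added at each of 14 ranks; step 3 of the working shows that it is not. A reader might also infer that one borderline P opens all later ranks. Under SAP 10.0 it opens only the next, and that rank must pass on its own result before testing goes on.

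**Conclusion.** The point holds, at minor priority. As written, the default rule in Protocol 8.1.1 and SAP 8.1 has a nominal level of 0.0505 and governs the 14 ranked secondary endpoints. Whether it also governs the co-primaries cannot be settled from the text.

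The consequence is confined to P values above 0.0500 and below 0.0505. The conclusion assumes P values uniform under the null and, for the conflict with the 95% CI, an interval from the same model as the test. It does not call the sample size or the planned power into question.

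**What to change.** In Protocol 8.1.1 and SAP 8.1, state that the co-primary and ranked secondary tests are judged on the unrounded P value (P ≤ 0.05), and that rounding to three decimals is for display only. This restores the stated level, settles how SAP 8.3.3 is to be read, and aligns each test with its 95% CI. It takes one sentence in each document, with the small power cost shown in the working.

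Timing affects the route. SAP 2.5 makes the end-of-placebo-period analysis the only one for these endpoints, and the endometrial biopsy text in Protocol 5.3.1.1 says that all subjects are past Month 36. The documents do not say whether that analysis has been run. If it has, rewriting the criterion would be a post-hoc change. In that case, leave the rule as it stands, give unrounded P values in the study report, and state whether any tested endpoint fell above 0.0500 and below 0.0505.

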8.2 Handling of Missing Data

Missing data will be imputed using the following methods for the efficacy analyses:

- Last Observation Carried Forward (LOCF): The LOCF analyses will use the completed evaluation from the previous post-baseline evaluation to impute missing data at the current evaluations. Values will only be carried forward if a subject prematurely discontinues and if the analysis month is equal to or after the month in which the subject prematurely discontinued. For Month 1 analysis, only observed cases will be used.
- Mixed-Effect Model Repeat Measurement (MMRM): The repeated measures analysis will be conducted using a mixed model including observed measurements at all visits. The mixed model includes the categorical fixed effects of treatment, visit and treatment-by-visit interaction, and the continuous fixed covariate of baseline measurement. An unstructured variance covariance matrix will be used. Parameter estimation is based on the assumption of data being missing at random and using the method of restrictive maximum likelihood (REML).
- Observed Cases (OC): The OC analysis will not impute values for missing evaluations, and thus a subject who does not have an evaluation on a scheduled visit will be excluded from the OC analysis for that visit. OC will exclude values after a subject prematurely discontinues from study drug.

8.3 Primary Efficacy Endpoint(s) and Analyses

8.3.1 Primary Efficacy Endpoint(s)

The co-primary efficacy endpoints will be the proportion of responders at Month 6 based upon the mutually-exclusive scales for daily assessment of Dysmenorrhea (DYS) and Non-Menstrual Pelvic Pain (NMPP) measured by the 4-point Endometriosis Daily Pain Impact Diary. Use of protocol specific rescue analgesic medication for endometriosis-associated pain as collected in the daily e-Diary will also be included in the responder definition.

For each of the co-primary endpoints, a subject is considered as a responder at Month 6 if (1) she has an absolute reduction of X or greater from baseline in average pain scores (DYS or NMPP) at Month 6; and (2) she has stable or decreased rescue analgesic use as defined in [Table 1](#) at Month 6. The pain threshold (i.e., the value of X) will be determined based on a Receiver Operating Characteristics (ROC) analysis using the PGIC assessment at Month 6 as an anchor and change from baseline in average pain score (DYS or NMPP) at Month 6 as the independent variable. All ROC analyses will be conducted prior to blind break and will contain all randomized subjects who receive at least 1 dose of study drug. Thresholds obtained for Month 6 will be used for all monthly visits during the 12-month placebo-controlled Treatment Period, i.e., the threshold obtained for Dys at Month 6 will be used for Dys at Months 1 – 12. The details of the ROC analysis are presented in [Appendix A](#) and the pain threshold values (X) are presented in [Appendix C](#).

Table 1. Analgesic Change During the Placebo-Controlled Treatment Period

Use of No Analgesics at Baseline		
Analgesic used at Baseline	Analgesic dose status at End of Time Window	Responder?*
None	None	Responder
	Opioid analgesic and/or NSAID is started	Nonresponder
Use of Only NSAID at Baseline		
Analgesic used at Baseline	Analgesic dose status at End of Time Window	Responder?*
NSAID	Dose stopped, decreases, or is stable**	Responder
	Dose increases by 15% or more	Nonresponder
	Opioid analgesic is substituted or added	Nonresponder
Use of Only Opioid Analgesic at Baseline		
Analgesic used at Baseline	Analgesic dose status at End of Time Window	Responder?*
Opioid analgesic	Dose stopped, decreases, or is stable**	Responder
	Dose stopped and NSAID substituted (any dose)	Responder
	Dose decreases and NSAID added (any dose)	Responder
	Dose stable** and NSAID added (any dose)	Nonresponder
	Dose increases by 15% or more	Nonresponder
Use of NSAID and Opioid Analgesic at Baseline		
Analgesics used at Baseline	Analgesic dose status at End of Time Window	Responder?*
NSAID + opioid analgesic	NSAID dose stops + opioid analgesic use stops, decreases, or is stable**	Responder
	NSAID use stops + opioid analgesic dose increases by more than 15%	Nonresponder
	NSAID dose decreases + opioid analgesic use stops, decreases, or is stable**	Responder

Table 1. Analgesic Change During the Placebo-Controlled Treatment Period (Continued)

Use of NSAID and Opioid Analgesic at Baseline		
Analgesics used at Baseline	Analgesic dose status at End of Time Window	Responder?*
	NSAID dose decreases + opioid analgesic dose increases by more than 15%	Nonresponder
	NSAID dose stable** + opioid analgesic use stops, decreases, or is stable**	Responder
	NSAID dose stable** + opioid analgesic dose increases by more than 15%	Nonresponder
	NSAID dose increases by more than 15% + opioid analgesic use stops	Responder
	NSAID dose increases by more than 15% + opioid analgesic dose decreases	Responder
	NSAID dose increases by more than 15% + opioid analgesic dose is stable**	Nonresponder
	NSAID dose increases by more than 15% + opioid analgesic dose increases by 15% or more	Nonresponder

* Responder = Defined as a subject who meets the protocol-specified pain score criteria for no increase in analgesic use.

** Stable = Dose is the same as the screening dose or increases by less than 15% of the screening dose.

Dysmenorrhea (DYS) and Non-Menstrual Pelvic Pain (NMPP)

Daily instances when subjects respond "Yes" to the question "Did you have your period in the last 24 hours" is counted as a day with reported DYS. Pain reported daily in response to the e-Diary question "On the next screen, choose the item that best describes your pain during the last 24 hours when you had your period" is referred in this document as DYS related pain. Daily instances when subjects respond "No" to the question "Did you have your period in the last 24 hours" is counted as a day with reported NMPP. Pain reported daily in response to the e-Diary question "On the next screen, choose the item that best describes your pain during the last 24 hours without your period" is referred in this document as NMPP related pain.

For both DYS and NMPP, responses of "None," "Mild," "Moderate," and "Severe" will be assigned a score of 0, 1, 2, and 3, respectively.

The monthly average pain score for DYS will be based on averaging the daily pain score over the number of days when the subject reported DYS related pain within each respective time window. The monthly average pain score for NMPP will be based on averaging the daily pain scores over the number of days when the subject reported NMPP related pain within each respective time window. If the subject's monthly average pain score (DYS or NMPP) is missing because the subject reported only the other kind of pain (mutually exclusive daily pain impact scale) in the corresponding time frame of interest (e.g., Month 6 DYS score is missing because the subject only reported NMPP during Month 6 analysis window), then the monthly average pain score for the relevant parameter (DYS or NMPP) will be set to 0 (zero).

Rescue Analgesic Use

For each class of rescue analgesics (NSAIDs and Opioids), analgesic use for each defined monthly period during the 12-month placebo-controlled Treatment Period will be based on the average pill count as collected in the daily e-Diary. The monthly average pill count for each class of rescue analgesics will be calculated by dividing the total pill count for the corresponding class of rescue analgesic by the length of the analysis window. For each class of rescue analgesic, if no analgesic use is reported for a period of interest, but e-Diary information is available for the corresponding time period, then the average pill count for the corresponding class of rescue analgesic use will be set to 0 (zero).

8.3.2 Handling of Missing Data for the Primary Efficacy Endpoints

For the co-primary endpoints, subjects who prematurely discontinue at or prior to Month 6 will have their average pain scores (DYS and NMPP) and rescue analgesic use carried forward (LOCF) from the last month in which both monthly average pain score (DYS and NMPP) and analgesic use are observed.

8.3.3 Primary Efficacy Analysis

The primary null hypothesis for this study is that there is no difference in the proportion of responders for each co-primary efficacy endpoint at Month 6 between elagolix plus E2/NETA and placebo. The null hypothesis will be tested against the alternate hypothesis that there is a difference between elagolix plus E2/NETA and placebo in the proportion of responders for each co-primary efficacy endpoint at Month 6.

Elagolix plus E2/NETA will be considered statistically more efficacious than placebo for the co-primary endpoint if and only if the two-sided P value for the comparison of the proportion of responders for both DYS and NMPP is less than or equal to 0.05 and in favor of elagolix plus E2/NETA.

The primary analysis of each of the co-primary endpoints will be based on a logistic regression model with the responder/non-responder categorization as the dependent variable, treatment as the main effect, and baseline pain score (DYS or NMPP) as the covariate. Elagolix plus E2/NETA will be compared to placebo for each of the co-primary endpoints. The proportion of responders, difference in proportions between each elagolix group and placebo, and odds ratio with corresponding 95% confidence intervals (CIs) and P values will be presented.

8.3.4 Additional Analyses of the Primary Efficacy Endpoint(s)

The following sensitivity analyses for each of the co-primary endpoints of the proportion of responders at Month 6 in pain scores will be conducted:

1. The difference between the elagolix plus E2/NETA and placebo in response rates will be analyzed using a chi-square test with a corresponding 95% CI for the difference in response rate based on normal approximation to the binomial distribution.
2. All subjects who prematurely discontinue the study drug at or before Month 6 will be considered as non-responders and the primary analysis will be repeated.

3. The primary analysis will be repeated using mixed-imputation. In particular, subjects who discontinue prior to or at Month 6 due to an adverse event (AE) or lack of efficacy will be considered non-responders, while subjects who discontinue prior to or at Month 6 due to other reasons will have their monthly pain score carried forward following the LOCF rule.
4. All subjects who switched NSAIDs use at Baseline, Month 6, or from Baseline to Month 6 will be considered as non-responders and the primary analysis will be repeated.
5. All subjects who switched NSAIDs use at Baseline, Month 6, or from Baseline to Month 6 will be excluded from the primary analysis.
6. The following rules will be used to standardize different NSAIDs use and opioid use. The standardized rescue analgesic use will be re-evaluated based on [Table 1](#) and the primary analysis will be repeated.
 - NSAID: 1 pill Naproxen = 1 pill Ibuprofen = 1 pill Diclofenac = 4 pills Celecoxib = 1 pill of NSAIDs use
 - Opioid: 1 pill hydrocodone + acetaminophen = 1 pills codeine phosphate + acetaminophen = 1 pill of opioid use

